6.3.3 Central reading of scans

An independent review of all scans used in the assessment of tumours according to RECIST will be conducted. All imaging assessments including unscheduled visit scans will be collected on an ongoing basis and sent to an AstraZeneca appointed Contract Research Organisation (CRO) for central analysis. Results of this independent review will not be communicated to investigators, and the management of patients will be based solely upon the results of the RECIST assessment conducted by the investigator.

A sensitivity analysis for this study will be based on the independent central review (ICR) of the radiological scans.

6.4 Safety

The Principal Investigator is responsible for ensuring that all staff involved in the study are familiar with the content of this section.

6.4.1 Definition of adverse events

An adverse event is the development of an undesirable medical condition or the deterioration of a pre-existing medical condition following or during exposure to a pharmaceutical product, whether or not considered causally related to the product. An undesirable medical condition can be symptoms (e.g., nausea, chest pain), signs (e.g., tachycardia, enlarged liver) or the

Date 05 November 2021

abnormal results of an investigation (e.g., laboratory findings, electrocardiogram). In clinical studies, an AE can include an undesirable medical condition occurring at any time, including run-in or washout periods, even if no study treatment has been administered.

The term AE is used to include both serious and non-serious AEs.

6.4.2 Definitions of serious adverse event

A serious adverse event is an AE occurring during any study phase (i.e., run-in, treatment, washout, follow-up), that fulfils one or more of the following criteria:

- Results in death
- Is immediately life-threatening
- Requires in-patient hospitalisation or prolongation of existing hospitalisation
- Results in persistent or significant disability/incapacity or substantial disruption of the ability to conduct normal life functions
- Is a congenital abnormality or birth defect
- Is an important medical event that may jeopardise the patient or may require medical intervention to prevent one of the outcomes listed above.

For further guidance on the definition of a SAE, see [Appendix B](#) to the Clinical Study Protocol.

6.4.3 Olaparib adverse events of special interest

Adverse events of special interest [AESI] are events of scientific and medical interest specific to the further understanding of olaparib's safety profile and require close monitoring and rapid communication by the investigators to AstraZeneca. Adverse Events of Special Interest for olaparib are the Important Identified Risk of MDS/AML and the Important Potential Risks of new primary malignancy (other than MDS/AML) and pneumonitis.

6.4.4 Recording of adverse events

Time period for collection of adverse events

Adverse Events, including Serious Adverse Events, will be collected from time of signature of informed consent*, throughout the treatment period and up to and including the 30-day follow-up period. All ongoing and any new AEs/SAEs identified during the 30 calendar days follow up period after last dose of study medication must be followed to resolution. After any interim analysis, any ongoing AEs/SAEs need to be unlocked and followed for resolution.

*Exception: In screening part 1 only SAEs related to study procedures must be reported (AEs do not require reporting). From screening part 2 onwards - all AEs/SAEs must be reported.

Date 05 November 2021

Follow-up of unresolved adverse events

Any SAE or non-serious adverse event that is ongoing at the time of the 30 day follow up, must be followed up to resolution unless the event is considered by the investigator to be unlikely to resolve, or the patient is lost to follow-up

AstraZeneca retains the right to request additional information for any patient with ongoing AE(s)/SAE(s) at the end of the study, if judged necessary.

Post Follow-up adverse events

For Pharmacovigilance purposes and characterisation of events of special interest, any case of MDS/AML or new primary malignancy occurring after the 30 day follow up period should be reported as SAE (or AE for non-melanoma skin cancers, if at least one of the criteria for SAE is not met, see Section 6.4.2) to AstraZeneca Patient Safety regardless of investigator's assessment of causality or knowledge of the treatment arm. A Questionnaire will be sent to any investigator reporting MDS/AML or new primary malignancy as an aid to provide detailed information on the case.

At any time after a patient has completed the study, if an Investigator learns of any SAEs, including death, and he/she considers there is a reasonable possibility that the event is causally related to the investigational product, the investigator should notify AstraZeneca, Patient Safety.

If patients who are gaining clinical benefit are allowed to continue study treatment post data cut off and / or post study completion then all SAEs must continue to be collected and reported to Patient Safety within the usual timeframe.

Otherwise, after study treatment completion (i.e. after any scheduled post treatment follow-up period has ended) there is no obligation to actively report information on new AEs or SAEs occurring in former study patients. This includes new AEs/SAEs in patients still being followed up for survival but who have completed the post treatment follow up period (30 days).

Variables

The following variables will be collected for each AE:

- AE (verbatim)
- The date when the AE started and stopped
- Changes in CTCAE grade
- Whether the AE is serious or not
- Investigator causality rating against the Investigational Product (yes or no)

Date 05 November 2021

- Action taken with regard to investigational product
- Outcome.

In addition, the following variables will be collected for SAEs:

- Date AE met criteria for serious AE
- Date Investigator became aware of serious AE
- AE is serious due to
- Date of hospitalisation
- Date of discharge
- Probable cause of death
- Date of death
- Autopsy performed
- Causality assessment in relation to study procedure(s)
- Causality assessment in relation to other medication
- Description of AE.

Severity of AE

For each episode on an adverse event, all changes to the CTCAE grade attained as well as the highest attained CTC grade should be reported.

It is important to distinguish between serious and severe AEs. Severity is a measure of intensity whereas seriousness is defined by the criteria in Section 6.4.2. An AE of severe intensity need not necessarily be considered serious. For example, nausea that persists for several hours may be considered severe nausea, but not a SAE. On the other hand, a stroke that results in only a limited degree of disability may be considered a mild stroke but would be an SAE (this would be recorded as an SAE as per the guidance found in this section (Section 6.4.4)).

The grading scales found in the National Cancer Institute (NCI) CTCAE version 4.0 will be utilised for all events with an assigned CTCAE grading. For those events without assigned CTCAE grades the recommendation is that the CTCAE criteria that convert mild, moderate and severe events into CTCAE grades should be used.

Date 05 November 2021

A copy of the CTCAE version can be downloaded from the [Cancer Therapy Evaluation Program](#) website.

Causality collection

The Investigator will assess causal relationship between Investigational Product and each Adverse Event, and answer 'yes' or 'no' to the question 'Do you consider that there is a reasonable possibility that the event may have been caused by the investigational product?'

For SAEs causal relationship will also be assessed for other medication and study procedures. Note that for SAEs that could be associated with any study procedure the causal relationship is implied as 'yes'.

A guide to the interpretation of the causality question is found in [Appendix B](#) to the Clinical Study Protocol.

Adverse Events based on signs and symptoms

All AEs spontaneously reported by the patient or reported in response to the open question from the study personnel: '*Have you had any health problems since the previous visit/you were last asked?*', or revealed by observation will be collected and recorded in the CRF. When collecting AEs, the recording of diagnoses is preferred (when possible) to recording a list of signs and symptoms. However, if a diagnosis is known and there are other signs or symptoms that are not generally part of the diagnosis, the diagnosis and each sign or symptom will be recorded separately.

Adverse Events based on examinations and tests

The results from protocol mandated laboratory tests and vital signs will be summarised in the clinical study report. Deterioration as compared to baseline in protocol-mandated laboratory values, vital signs should therefore only be reported as AEs if they fulfil any of the SAE criteria or are the reason for discontinuation of treatment with the investigational product.

If deterioration in a laboratory value/vital sign/ECG is associated with clinical signs and symptoms, the sign or symptom will be reported as an AE and the associated laboratory result/vital sign/ECG will be considered as additional information. Wherever possible the reporting investigator uses the clinical, rather than the laboratory term (e.g., anaemia versus low haemoglobin value). In the absence of clinical signs or symptoms, clinically relevant deteriorations in non-mandated parameters should be reported as AE(s).

Deterioration of a laboratory value, which is unequivocally due to disease progression, should not be reported as an AE/SAE.

Any new or aggravated clinically relevant abnormal medical finding at a physical examination as compared with the baseline assessment will be reported as an AE.

Date 05 November 2021

NB. Cases where a patient shows an AST or ALT $\geq 3 \times \text{ULN}$ or total bilirubin $\geq 2 \times \text{ULN}$ may need to be reported as SAEs, please refer to [Appendix D](#) ‘Actions required in cases of combined increase of Aminotransferase and Total Bilirubin – Hy’s Law’, for further instructions.

Disease progression

Disease progression can be considered as a worsening of a patient’s condition attributable to the disease for which the investigational product is being studied. It may be an increase in the severity of the disease under study and/or increases in the signs and symptoms of the cancer. The development of new, or progression of existing metastasis to the primary cancer under study should be considered as disease progression and not an AE. Events, which are unequivocally due to disease progression, should not be reported as an AE during the study.

New cancers

The development of a new primary cancer (including skin cancer) should be regarded as an AE and will generally meet at least one of the serious criteria (see Section [6.4.2](#)). New primary cancers are those that are not the primary reason for the administration of the study treatment and have developed after the inclusion of the patient into the study. They do not include metastases of the original cancer. Symptoms of metastasis or the metastasis itself should not be reported as an AE/SAE, as they are considered to be disease progression.

Lack of efficacy

When there is deterioration in the ovarian cancer, for which the study treatment(s) is being used, there may be uncertainty as to whether this is lack of efficacy or an AE. In such cases, unless the Sponsor or the reporting physician considers that the study treatment contributed to the deterioration of the condition, or local regulations state to the contrary, the deterioration should be considered to be a lack of efficacy and not an AE.

Deaths

All deaths that occur in screening part 1 related to study procedures should be reported as a SAE.

All deaths that occur from screening part 2 onwards, including within the protocol-defined 30-day post-study follow-up period after the administration of the last dose of study treatment, must be reported as follows:

- Death clearly the result of disease progression should be reported to the study monitor at the next monitoring visit and should be documented in the DEATH eCRF but should not be reported as an SAE.
- Where death is not due (or not clearly due) to progression of the disease under study, the AE causing the death must be reported to the study monitor as a SAE within **24 hours** (see Section [6.4.5](#) for further details). The report should contain a comment regarding the co-involvement of progression of disease, if appropriate,

Date 05 November 2021

and should assign main and contributory causes of death. This information can be captured in the 'death eCRF'.

- Deaths with an unknown cause should always be reported as a SAE. A post mortem maybe helpful in the assessment of the cause of death, and if performed a copy of the post-mortem results should be forwarded to AstraZeneca within the usual timeframes.

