5.5.5 Management of toxicity of study treatment

Any toxicity observed during the study treatment phase could be managed by interruption of the dose of study treatment if deemed appropriate by the Investigator. Repeat dose interruptions are allowed as required, for a maximum of 14 days on each occasion. If the interruption is any longer than this the AstraZeneca study team must be informed. Study treatment must be interrupted until the patient recovers completely or the toxicity reverts to the National Cancer Institute (NCI) Common Terminology Criteria for Adverse Events (current version) grade 1 or less.

Where toxicity reoccurs following re-challenge with study treatment, and where further dose interruptions are considered inadequate for management of toxicity, then the patient should be considered for dose reduction or must permanently discontinue study treatment. Treatment must be interrupted if any NCI-CTCAE grade 3 or 4 adverse event occurs which the Investigator considers to be related to administration of study treatment.

NB. In case a patient shows an AST or ALT $\geq 3xULN$ or total bilirubin $\geq 2xULN$ please refer to [Appendix D](#) ‘Actions required in cases of combined increase of Aminotransferase and Total Bilirubin – Hy’s Law’, for further instructions.

Management of anaemia:

Adverse events of anaemia CTCAE grade 1 or 2 (Haemoglobin (Hb) ≥ 8 g/dl) should be investigated and managed as deemed appropriate by the investigator with or without interruption of study drug or change in dose, taking into account previous history of anaemia. Common treatable causes of anaemia (e.g. iron, vitamin B12 or folate deficiencies and hypothyroidism) should be excluded. In some cases management of anaemia may require

Date 05 November 2021

blood transfusions. However, if patient develops anaemia CTCAE grade 3 (Hb < 8g/dl) or worse, study treatment should be interrupted for up to maximum of 4 weeks to allow for bone marrow recovery and patient should be managed appropriately. Study treatment can be restarted at the same dose if Hb has recovered to ≥ 9 g/dl. Any subsequently required anemia related interruptions, considered likely to be dose related, or coexistent with newly developed neutropenia, and or thrombocytopenia, will require study treatment dose reductions to 250 mg bd as a first step and to 200 mg bd as a second step.

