If a patient has been treated for anaemia with multiple blood transfusions without study treatment interruptions and becomes blood transfusion dependant as judged by investigator, study treatment should be interrupted for up to a maximum of 4 weeks to allow for bone marrow recovery. Study treatment should be restarted at a reduced dose.

Management of neutropenia and leukopenia:

Adverse event of neutropenia and leukopenia should be managed as deemed appropriate by the investigator with close follow up and interruption of study drug if CTC grade 3 or worse neutropenia occurs.

Study treatment can be interrupted for CTCAE Grade 1 or 2 neutropenia as per investigator's judgement. In the case of CTCAE Grade 3 or 4 neutropenia, study treatment should be interrupted for a maximum of 4 weeks.

Study treatment can be restarted at the same dose if an AE of neutropenia or leukopenia has recovered to CTCAE Grade 1 or below (absolute neutrophil count $\geq 1.5 \times 10^9/L$).

Primary prophylaxis with Granulocyte colony-stimulating factor (G-CSF) is not recommended, however, if patient develops febrile neutropenia, study treatment should be stopped and appropriate management including G-CSF should be given according to local hospital guidelines. Please note that G-CSF should not be used within at least 24 hours of the last dose of study treatment unless absolutely necessary. Growth factor support should be stopped at least 24 hours before restarting study treatment (7 days for pegylated G-CSF).

Any subsequent interruptions will require study treatment dose reductions to 250 mg bd as a first step and to 200 mg bd as a second step.

Management of thrombocytopenia

An adverse event of thrombocytopenia should be managed as deemed appropriate by the investigator. If patient develops thrombocytopenia CTCAE grade 3 or worse study treatment should be interrupted for a max of 4 weeks. In some cases management of thrombocytopenia may require platelet transfusions. Platelet transfusions should be done according to local hospital guidelines.

Management of prolonged haematological toxicities while on study treatment:

If patient develops prolonged haematological toxicity such as:

Date 05 November 2021

- ≥ 2 week interruption/delay in study treatment due to CTC grade 3 or worse anaemia and/or development of blood transfusion dependence
- ≥ 2 week interruption/delay in study treatment due to CTC grade 3 or worse neutropenia ($ANC < 1 \times 10^9/L$)

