6.4.6 Laboratory safety assessment

Blood and urine samples for determination of clinical chemistry, haematology, coagulation, and urinalysis will be taken at the times indicated in the Study Schedule (see [Table 1](#), [Table 2](#) and [Table 3](#)).

Date 05 November 2021

These tests will be performed by the hospital's local laboratory. Additional analyses may be performed if clinically indicated.

Any clinically significant abnormal laboratory values should be repeated as clinically indicated and recorded on the eCRF.

The following laboratory variables will be measured:

6.4.6.1 Full haematology assessments for safety;

- haemoglobin,
- red blood cells [RBC]
- platelets
- mean cell volume [MCV]
- mean cell haemoglobin concentration [MCHC],
- mean cell haemoglobin [MCH],
- white blood cells [WBC],
- absolute differential white cell count
 - (neutrophils, lymphocytes, monocytes, eosinophils and basophils) and absolute neutrophil count or segmented neutrophil count and Band forms should be performed at each visit and when clinically indicated. If absolute differentials not available please provide % differentials.

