AEs will be assigned CTCAE grades (National Cancer Institute (NCI) CTCAE version 4.0) and summaries of the number and percentage of patients will be provided by maximum reported CTCAE grade, system organ class, preferred term and actual treatment group. Fluctuations observed in CTCAE grades during study will be listed.

Summaries of the number and percentage of patients with AEs leading to dose modification of olaparib/placebo by preferred term and treatment group will be presented for the following:

- AEs leading to a dose reduction of olaparib/placebo
- AEs leading to a dose interruption of olaparib/placebo
- AEs leading to a dose modification, defined as a dose interruption and/or dose reduction of olaparib/placebo.

In addition, AEs with outcome of death, SAEs, AEs leading to discontinuation of treatment, AEs causally related to olaparib/placebo and OAEs will be listed.

A summary of deaths will be provided with number and percentage of patients by actual treatment group, categorised as:

- Death related to disease under investigation only
- Death related to disease under investigation only (death > 30 days after last treatment dose)
- AE with outcome of death only
- AE related to disease under investigation and with AE outcome of death
- AE with outcome of death only (AE start date falling >30 days after last treatment dose)
- Deaths > 30 days after last treatment dose, unrelated to AE or disease under investigation
- Deaths >30 days after last treatment dose, AE related to disease under investigation and with AE outcome of death,
- Patients with unknown reason for death.

A corresponding listing will also be produced.

A separate summary will be produced that presents any events that occur prior to dosing or starting more than 30 days after discontinuing therapy.

Summary tables will also be produced for the following common adverse events, based on grouped preferred terms:

- Anaemia
- Neutropenia
- Thrombocytopenia
- Nausea
- Vomiting
- Fatigue/Asthenia

The specific preferred terms to be included in the summaries will be provided prior to database lock.

Summary of long term tolerability

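### The laboratory reporting rule can keep symptom-free cytopenias that change dosing out of the AE tables meant to count them

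*Protocol*

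**What the plan says.** Protocol 6.4.4, under AEs based on examinations and tests, explains that mandated laboratory results will be summarised in the study report. It concludes that deteriorations in them "should therefore only be reported as AEs if they fulfil any of the SAE criteria or are the reason for discontinuation of treatment". If signs or symptoms accompany the change, the sign or symptom is the AE.

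Haematology is a mandated test. Under Protocol 6.4.6, "Blood and urine samples for determination of clinical chemistry, haematology, coagulation, and urinalysis will be taken at the times indicated" in the study schedule.

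Protocol 5.5.5 manages the same findings as adverse events, and its thresholds are laboratory ones:

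- **Anaemia:** at haemoglobin below 8 g/dl, "study treatment should be interrupted for up to maximum of 4 weeks to allow for bone marrow recovery".
- **Thrombocytopenia:** "If patient develops thrombocytopenia CTCAE grade 3 or worse study treatment should be interrupted for a max of 4 weeks".
- **Neutropenia:** grade 3 or 4 likewise leads to interruption.
- **Dose reduction:** the anaemia and neutropenia paragraphs go on to dose reduction when interruptions recur. The anaemia paragraph attaches conditions to this.

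None of these steps requires a symptom.

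SAP 4.2.11 then plans summaries of AEs of CTCAE grade 3 or higher, of AEs leading to interruption, of AEs leading to reduction, and of "AEs leading to a dose modification, defined as a dose interruption and/or dose reduction of olaparib/placebo". It also plans tables of anaemia, neutropenia and thrombocytopenia built from grouped preferred terms. All of these count reported AEs.

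**The concern.** The two protocol sections give a site different answers to the same question: is a symptom-free grade 3 platelet count that pauses the drug to be recorded as an AE? Section 6.4.4 says no unless it is serious or ends treatment. Section 5.5.5 speaks of it as an AE throughout.

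Protocol 1.1.5 names bone marrow as the primary target organ of toxicity, so cytopenias that change dosing are central to the safety account of this drug. If some sites follow one section and some the other, the AE tables under-count such events by an unknown amount. They may also disagree, without explanation, with the laboratory shift tables and with the exposure summaries of reasons for dose changes. If olaparib causes more such cytopenias than placebo, which the toxicology gives reason to expect, the under-count would fall more on olaparib.

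**Working it through.** No formula applies. The check traces the reporting rule through the other sections.

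1. **Does the rule reach cytopenias?** Yes. Haematology is on the mandated list in Protocol 6.4.6. Section 6.4.4 is less restrictive for non-mandated parameters, where a clinically relevant symptom-free deterioration is an AE. That does not help here.

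2. **Does a dose-changing cytopenia meet either limb of the rule?** Not as such. Interruption and reduction are not discontinuation. No SAE criterion in Protocol 6.4.2 refers to laboratory grade, dose action or transfusion. Some cases could qualify through hospitalisation or through the judgement-based criterion "Is an important medical event that may jeopardise the patient or may require medical intervention to prevent one of the outcomes listed above". The rest meet neither limb.

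3. **Does another section add a reporting trigger?** None was found. The preference in 6.4.4 for the clinical over the laboratory term (anaemia rather than low haemoglobin) governs naming. The events of special interest in 6.4.3 are MDS/AML, new primary malignancy and pneumonitis. Section 5.5.5 calls cytopenias adverse events but gives no recording instruction.

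4. **Worked case.** Take a scheduled sample with platelets below 50 x 10^9/L, no symptoms, not judged serious, drug paused and later resumed.

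| Output | Site follows 6.4.4 | Site follows 5.5.5 wording |
|---|---|---|
| Grade 3 or higher AEs | not counted | counted |
| AEs leading to interruption | not counted | counted |
| AEs leading to modification | not counted | counted |
| Grouped thrombocytopenia AEs | not counted | counted |
| Laboratory shift table (worst grade) | counted | counted |
| Exposure summary of reasons for interruption | counted | counted |

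The same patient is in or out of four AE tables depending on which section the site read.

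5. **Do the other outputs close the gap?** In part.
 - SAP 4.2.11 gives shift tables by worst grade and lists flagged clinically significant results, but neither shows what the result led to.
 - SAP 4.2.13 summarises reasons for dose changes, but not against laboratory grade.
 - Protocol 5.6 and 6.2.2 have transfusions recorded, but no planned table ties them to a laboratory value.
 - Protocol 6.4.4 collects the action taken with study drug for each AE, so without an AE record that link is absent.

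6. **Size.** The documents give no rate, in either arm, of symptom-free cytopenia leading to interruption, reduction or transfusion. The under-count cannot be computed from them.

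**The case against.** The best defence is that 6.4.4 states its reason: mandated laboratory results are reported separately, so duplicating them as AEs is unnecessary. Shift tables, flagged listings, recorded reasons for every interruption and reduction, and transfusion records all exist. The review for other significant AEs (Protocol 11.2.1, SAP 3.4.1) will examine laboratory data, and its own examples include marked haematological abnormalities and events leading to dose reduction. This stands in part: the underlying data are not lost. But that review classifies by expert judgement and is not a systematic count, and no planned output joins laboratory grade to dose action.

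A second defence is that sites will read 5.5.5 and report these events anyway. That also has force. Inconsistent capture is more likely than loss of every case.

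A reader might go further and infer that the general rule, "Treatment must be interrupted if any NCI-CTCAE grade 3 or 4 adverse event occurs which the Investigator considers to be related" to study treatment, could never be triggered by a laboratory-only finding. The documents do not support that. Section 6.4.4 limits what is reported. The definition of an AE in Protocol 6.4.1 includes abnormal laboratory findings, and 5.5.5 gives cytopenias their own grade-based interruption rules that do not depend on an AE report.

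A last objection is timing. Global enrolment closed on 14 November 2014 and treatment is nominally limited to two years, so rewording 6.4.4 in a protocol dated November 2021 can affect only patients still dosing. That is correct, and it is why the SAP table comes first in the fix.

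**Conclusion.** The point stands as an inconsistency in reporting. Applied as written, 6.4.4 leaves a non-serious, symptom-free cytopenia that interrupts or reduces dosing without an AE record, and the SAP 4.2.11 tables that count reported AEs can under-count accordingly. This assumes that at least some sites followed 6.4.4 literally, which the documents neither confirm nor exclude.

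The size is unknown. A reader might put assumed percentages on each arm and arrive at a number of missing patients, mostly on olaparib. Such a figure would only restate the assumption. Nor do the documents support saying that these events vanish from the safety report: they leave the AE tables, not every output. For transfusion the claim is narrower still. Some transfused patients would qualify as SAEs, and no table of AEs leading to transfusion is planned, so cases managed by transfusion alone affect only the graded AE and grouped cytopenia tables.

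One linked display is missing, and the reporting rule needs to be made consistent. Both are worth doing, and neither bears on the efficacy conclusions.

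**What to change.** **SAP 4.2.11.** Add one table by actual treatment group in the safety analysis set, drawn from laboratory, dosing and transfusion records. It should count patients with a grade 3 or higher haemoglobin, neutrophil or platelet value followed by interruption, reduction or transfusion, whether or not an AE was recorded. State beforehand how close in time the action must be to the sample. Splitting the count by whether a matching AE exists would show the size of any under-count directly. These data are already collected, and SAP 4.2.11 already has selected safety data re-summarised at each planned OS analysis, which is a natural place for the table.

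**Protocol 6.4.4, 5.5.5 and SAP 4.2.11.** Reconcile them so that, for patients still on treatment, a mandated laboratory deterioration leading to interruption or reduction is also recorded as an AE. Note the date of the change in the SAP and the study report, because capture rules will differ before and after it. The interruption and reduction rules themselves are for the sponsor and are not questioned here.

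**Cost.** One extra table, one reporting sentence and a few more non-serious AE records.
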